### **5. STUDY OBJECTIVES**

#### **5.1 Primary Objective**

To specifically illustrate and measure both clinical and empirical efficacy described by (AARC) in the Clinical Practices Guidelines for Postural Drainage Therapy (1991) for external manipulation of the thorax for postural drainage therapy and the secretion clearance, or presence of atelectasis caused by mucus plugging.

Outcome measured by:

Percentage change of oxygen levels in the blood (pulse oximetry). SpO2 will be monitored using the standard pulse oximeter system (K131111). Change from baseline before treatment and measure again up to 3.5 hours after treatment.

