# **6. STUDY DESIGN**

## **6.1 Description of the Protocol**

The present study is designed as a multi-center, non-randomized, single-blind, one arm group trial with 70 participants per arm.

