### **9.1.1 Efficacy Criteria**

Primary: Physical exam by medical practitioner for initial diagnosis and changes in spirometer reading from before treatment compared to reading three (3) hours after treatment. In addition, changes in iHealth Air pulse oximeter (FDA 510k K131111) reading from before treatment compared to reading three (3) hours after treatment.

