#### **9.1.1.1 Primary Criterion**

Composite success rate. Safety - no issues or reported adverse conditions.

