#### **13.4.1.3 General Statistical Approach**

All statistical tests will be two-sided.

All summary tables for quantitative parameters will display mean, standard deviation, median, range (minimum and maximum), as well as number of missing data (if relevant). All summary tables for qualitative parameters will display counts, percentages and number of missing data if relevant.

Baseline data are defined as the last measurement performed before the first study medical device intake.

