#### **13.7.1.2.3 Main Statistical Model and Adjustment for Covariates**

For the primary analysis, all adjudicated events occurring from randomization to the study end date (inclusive) will be counted, including events occurring after early permanent discontinuation of study medical device. The proportion of participants remaining event-free over time will be displayed in the form of survival curves using the Kaplan-Meier method and analyzed (primary analysis) using a two-sided log-rank test. Statistical significance will be claimed if the computed p-value is equal to or less than 0.05.

The number and percentage (crude rate) of participants experiencing a primary endpoint will be summarized.

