Statistical and Analytical Plan:

All study practices and statistical methods are based on the International Conference on Harmonization (ICH) document "Statistical Principles for Clinical Trials."

Data will be summarized by treatment group. Baseline characteristics, and safety outputs total overall columns will be included to summarize all subjects.

For all baseline, demographic, safety and efficacy outputs data will be summarized by treatment group.

In summary tables of continuous variables, the minimum and maximum statistics, the arithmetic mean and median, the 95% confidence interval, standard deviation, and standard error will be presented will to the same number of decimal places as the original data.

In summary tables of categorical variables, counts and percentages will be used. The denominator for each percentage will be the number of subjects within the population treatment group unless otherwise specified.

All hypothesis testing will be carried out at the 5% (2-sided) significance level unless otherwise specified.

P-values will be rounded to three decimal places. P-values less than 0.001 will be reported as <0.001 in tables.

At the conclusion of the trial, the raw data shall be analyzed by a blinded statistician of Mack Biotech, Corp. and then create a report with the clinical trial outcome.

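### The primary efficacy criterion is an undefined success rate that conflicts with the continuous SpO2 change in section 5.1 and the event analysis in section 13.7.1

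*Protocol*

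**What the plan says.** The protocol describes its primary efficacy measure in several ways.

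- Section 5.1 measures the primary objective by "Percentage change of oxygen levels in the blood (pulse oximetry"), taken before treatment and again up to 3.5 hours afterwards. Section 5.2 makes the change in FVC and FEV1 secondary.
- Section 9.1 describes the goal of the trial in terms of spirometry alone.
- Section 9.1.1 lists as primary a physical exam, the change in spirometer reading, and "changes in iHealth Air pulse oximeter (FDA 510k K131111) reading from before treatment compared to reading three (3) hours after treatment".
- Section 9.1.1.1, directly beneath, gives the primary criterion as "Composite success rate". It reads in full: "Composite success rate. Safety - no issues or reported adverse conditions". Section 9.1.1.2 puts percent spirometer change under the secondary criterion.
- Section 9.1.2.1, where the components of the primary endpoint should be defined, is marked not applicable.
- Sections 13.7 and 13.7.1 name a reduction in the appearance of cystic fibrosis.
- Section 13.7.1.1 defines a composite of first skin, allergic or new medical events. Section 13.7.1.2.3 analyses it by Kaplan-Meier curves and a log-rank test: "Statistical significance will be claimed if the computed p-value is equal to or less than 0.05".

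The SAP does not choose among these. It adds only general conventions, including the two-sided 5% level.

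**The concern.** A success rate requires each participant to be classed as a success or a failure. Within section 9 the only numeric primary efficacy data are the paired oximeter and spirometer readings, so the natural reading there is that some cut is applied to them. No clinical threshold, guideline or regulatory reason for a responder endpoint is given.

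Two things are at stake. First, the before/after contrast is the only efficacy information in a one-arm trial of 70, and a cut discards the size of each participant's change. Second, a responder proportion in one arm needs an external reference rate, and none is stated. A mean paired change has an obvious null value of zero.

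While the conflict stands, the sponsor could report any of several quantities as the primary result after seeing the data.

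**Working it through.** **1. Is there a planned figure to reproduce?** No. Section 13.2 gives 70 participants without an effect size, SD, success rate, reference rate or power. The planned log-rank test compares groups, and section 6.1 describes a "one arm group trial with 70 participants per arm". There is no second group, so no power, and no loss of power, can be computed for the stated primary analysis.

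**2. The two readings of success.**
- *Cut on the paired readings.* Supported by the position of 9.1.1.1 under the efficacy criteria and by 9.1.2, which gives before/after oximetry and spirometry as the primary assessment.
- *Freedom from adverse events.* Supported by the second sentence of 9.1.1.1 and by 13.7.1.1, the only composite with listed components. Under this reading, SpO2 does not enter the primary criterion.

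**3. What a cut would cost (illustration).** Inputs from the documents are n = 70 (section 6.1) and a two-sided 5% level. Protocol 13.4.1.3 says "All statistical tests will be two-sided" and the SAP says "All hypothesis testing will be carried out at the 5% (2-sided) significance level unless otherwise specified". Assumed, because the documents give nothing: standardised mean paired change d, normally distributed changes, one value per participant, no dropout.

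- Paired t-test: noncentral t with 69 df and noncentrality d × √70.
- Responder test: exact equal-tailed binomial, with cut c in SD units, p0 = Φ(−c) under no change and p1 = Φ(d − c). For c = 0, 0.5 and 1, p0 is 50%, 31% and 16%.
- Both of two readings improve: bivariate normal, correlation 0.5, equal effects, p0 = 1/3, compared with the t-test on one reading.

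Worked case, d = 0.30 and c = 0. Noncentrality is 0.30 × 8.367 = 2.51, giving t-test power of 69.7%. For the responder test p1 = Φ(0.30) = 0.618. It rejects at 44 or more (or, by symmetry, 26 or fewer) of 70, with an actual size of 4.1% and power of 48.0%. The loss is 21.7 points.

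Power in %, with the loss in points in brackets (losses taken before rounding):

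| d | Paired t | Cut 0 | Cut 0.5 SD | Cut 1 SD | Both improve |
|---|---|---|---|---|---|
| 0.25 | 54.1 | 35.2 (18.9) | 36.3 (17.8) | 31.3 (22.8) | 41.6 (12.5) |
| 0.30 | 69.7 | 48.0 (21.7) | 49.3 (20.4) | 42.8 (26.8) | 56.1 (13.6) |
| 0.35 | 82.3 | 61.0 (21.4) | 62.4 (20.0) | 55.1 (27.2) | 69.8 (12.5) |
| 0.40 | 91.0 | 72.8 (18.2) | 74.2 (16.8) | 66.9 (24.0) | 81.2 (9.8) |
| 0.50 | 98.5 | 89.6 (8.9) | 90.6 (7.9) | 85.6 (12.9) | 94.7 (3.8) |
| 0.60 | 99.9 | 97.2 (2.7) | 97.6 (2.2) | 95.5 (4.4) | 99.0 (0.8) |

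**4. Sensitivity.** Part of the gap at a zero cut comes from the conservatism of the exact test. By normal approximation the loss is 19.1 points at d = 0.30 and 16.0 at d = 0.40. For the both-improve rule at d = 0.30, the loss is 8.2 points with correlation 0 and 20.5 with correlation 0.8.

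**The case against.** A reader might infer that the plan does dichotomise SpO2 and spirometry, and that the trial therefore loses a definite amount of power, say 16 to 22 points. The documents do not support that. No section says the readings are cut. The sentence that follows the success rate concerns safety, 13.7.1.1 builds its composite from adverse events, 13.7.1.2.2 rules out transforming the raw data, and 5.1, 5.2 and 9.1.1.2 keep SpO2 and lung function as percentage changes. Nor is a one-sample binomial test planned anywhere. A single headline loss also hides how far the figure moves with the cut, the effect size and the way readings are combined. The rule in the table that is actually a composite loses least.

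This part of the objection stands: dichotomisation is an inference, and the power figures illustrate a choice the sponsor faces rather than measure the plan as written.

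The objection does not rescue the criterion. If success means freedom from adverse events, the primary efficacy criterion leaves out the very outcome that 5.1 calls primary. On either reading the criterion is undefined, conflicts with 5.1, and has no usable single-arm test.

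**Conclusion.** The point holds as a conflict over the primary endpoint. The success rate in 9.1.1.1 is undefined. It disagrees with the continuous SpO2 outcome in 5.1, and 13.7.1 supplies an event composite and a test that cannot be carried out in one arm. This rests on the text alone.

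The cost of a responder cut is conditional. For d between 0.25 and 0.40 it is about 17 to 27 points for single cuts at 0 to 1 SD, and about 10 to 14 points for a both-improve rule with correlation 0.5. Across all four criteria it falls to about 4 to 13 points at d = 0.5 and about 1 to 4 at d = 0.6. These figures assume normal changes, no dropout and an exact binomial test that the plan does not contain. The documents give no effect size that would place the trial in this range.

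The sponsor should correct this before analysis. Confidence is medium, because what was meant by success cannot be settled from the documents.

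**What to change.** Make these changes in one edit, so that 9.1.1.1, 13.7, 13.7.1 (with 13.7.1.1) and 13.7.1.2.3 agree.

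1. Define the primary efficacy endpoint as the within-participant change in SpO2 from before to after treatment, one value per participant. Section 8.11 pays per day of data sent, which implies repeated readings. State the rule for combining them, for example the mean over that participant's recorded sessions. Reconcile the post-treatment time, which is up to 3.5 hours in 5.1 and three hours in 9.1.1.
2. Report the mean change with its 95% CI and test it against zero with a two-sided paired t-test at 5%. Use the Wilcoxon signed-rank test as a sensitivity analysis. Replace the log-rank test, and adapt the censoring rule in 13.7.1.2.1 and the Cox model in 13.7.1.2.5, which belong to it.
3. Keep the FVC and FEV1 change as secondary, as in 5.2, and bring 9.1 and 9.1.1 into line with that.
4. Report any success rate as a descriptive percentage only. If a cut is used, state and justify it.
5. Move the skin, allergic and new-condition events to the safety analysis in 13.8.
6. Repeat the endpoint and test in the SAP.

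The cost is protocol and SAP wording, including the rule for repeated readings. No new participants, procedures or data are needed. The small downside is that a percent-successful figure is no longer the headline result, though it can still be tabulated.

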## **7. SELECTION OF PROCESS OF PARTICIPANTS**

### **7.1 Number of Participants Planned**

Based upon the anticipated event rates, premature treatment discontinuation and expected relative efficacy, approximately 70 participants will be enrolled in the study, with approximately 70 participants in each arm.

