### **8.3 Method of Assigning Participants to Treatment Group**

N/A - All included shall be assigned to the single arm.

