### **13.2 Determination of Sample Size**

Based on the targeted population for the study of 30,000 patients, 70 participants is considered a reasonable assumption for the yearly representational event rate in the group. Assuming recruitment over a 16 month period, and a total study duration of 24 months, 70 participants per group has been historically significant for prior trials designed to illustrate clear efficacy of a device as it relates to the United States CMS for this category of device.

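### Safety is expressed as the absence of reported adverse conditions and no planned output bounds a harm rate, although zero events in 70 participants would exclude only rates above about 4% to 5%

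*Protocol*

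**What the plan says.** The primary criterion in protocol section 9.1.1.1 names a composite success rate and then gives the safety clause: "Safety - no issues or reported adverse conditions". Section 9.1.2.1, where its components should be defined, is marked as not applicable.

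On reporting, protocol section 13.4.1.3 states: "All summary tables for qualitative parameters will display counts, percentages and number of missing data if relevant". Section 13.8.1.2 lists AE summaries as the number and percentage of participants. Sections 13.8.1.3 and 13.8.1.4 say only that deaths, SAEs and AEs leading to discontinuation will be summarized by organ class and preferred term. The SAP follows the same pattern: "In summary tables of categorical variables, counts and percentages will be used". It plans a 95% confidence interval for continuous variables only.

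The design is a "one arm group trial with 70 participants per arm", and section 8.3 confirms that "All included shall be assigned to the single arm". Section 7.1 says that "approximately 70 participants will be enrolled in the study". Section 13.4.1.2 uses the intent-to-treat (ITT) population for safety, whether or not a participant received the device.

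**The concern.** Absence of events in a small sample is weak evidence of absence of harm. How weak depends on the sample size, and an upper confidence limit shows it. Here the criterion is worded as absence, and the tables that would support it carry no interval. A result with no events of some type could be reported as a safety finding without saying what rates it leaves open.

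This matters because section 13.8 gives weight to balancing benefit against risk, and the plan supplies no bound for the risk side. With no control arm, the uncertainty cannot be carried by a between-group comparison either. An interval on the single-arm proportion is the natural way to express it.

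**Working it through.** **Is there a figure to reproduce?** No. Section 13.2 justifies the size by a target population of 30,000 and by precedent: "70 participants is considered a reasonable assumption for the yearly representational event rate in the group". Section 7.1 mentions anticipated event rates but gives none. There is no event rate, power or precision target, so 70 can be neither reproduced nor refuted as a safety sample size.

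**Inputs.** n = 70 (sections 6.1, 7.1 and 13.2). The true harm rate p per participant is not in the documents. I assume 1% as an illustration and show 0.5% to 5%.

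**1. What zero events would exclude.** This step needs no assumed harm rate.
- One-sided 95% upper bound: 1 − 0.05^(1/70) = 0.0419, or 4.2%.
- Two-sided 95% Clopper-Pearson upper limit: 1 − 0.025^(1/70) = 0.0513, or 5.1%.

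**2. Chance that a given harm is not seen at all.** P(0 of 70) = (1 − p)^70.

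| Assumed true rate p | P(no event in 70) |
|---|---|
| 0.5% | 0.704 |
| 1% | 0.495 |
| 2% | 0.243 |
| 3% | 0.119 |
| 5% | 0.028 |

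Treating the 70 as a sample without replacement from 30,000 changes the 1% figure only to 0.494. The rate with an 80% chance of at least one event in 70 is 1 − 0.2^(1/70) = 2.3%.

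**3. Effect of the denominator.** The ITT set can include people who never used the device. If 10% or 20% were unexposed (my assumption), 63 or 56 would be exposed. Zero events would then give upper limits of 4.6% one-sided and 5.7% two-sided for 63, and 5.2% and 6.4% for 56. The chance of missing a 1% harm rises to 0.531 and 0.570.

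**4. Why step 2 gives only ceilings on a clean result.** Section 10.1 has all AEs recorded, serious or not and related or not. If unrelated events also break the criterion, a clean trial needs neither kind. With an independent background AE rate b (assumed) and a 1% harm, P(clean) = (0.99 × (1 − b))^70. This is 0.245 for b = 1%, 0.120 for b = 2% and 0.014 for b = 5%.

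**5. Does another planned output supply a bound?** The composite of adverse events in section 13.7.1.1 gets Kaplan-Meier curves, a log-rank test and a crude rate (section 13.7.1.2.3), with no confidence limit specified for the rate. The 95% intervals in section 13.7.1.2.5 are for subgroup hazard ratios, which do not bound an absolute rate. Appendix 5 treats stopping for safety as a matter of judgment and sets no bound.

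**The case against.** A reader might infer that the trial would declare a 1% device harm free of issues about half the time. The documents do not support this, for two reasons.

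- **The criterion may not be a trial-level rule.** It opens with a composite success rate, and a rate is naturally a proportion of participants. The safety clause may be one component of each participant's success. In that case nothing is declared from a zero count across the trial. With the components undefined, neither reading can be established.
- **Passing a trial-level rule would be harder than the 49% suggests.** All AEs are recorded, in people with cystic fibrosis, and the clause is not limited to device-related events. The 49% is the chance that one assumed harm goes unseen. It equals the chance of a clean result only if nothing else is reported.

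A reader might also infer that a very low but nonzero count would be taken as safe. No section says so, and under a strict zero-event rule a single event would fail.

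Three further points are fair. Counts and percentages are ordinary for AE tables. Any study of 70 has a similar bound after zero events. Because counts and denominators are shown, a reader could derive the interval. Safety is also examined more widely than in section 9.1.1.1, through the SAE and discontinuation tables, the composite and the Data Monitoring Committee.

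These points remove the stronger headline but leave the gap. On either reading no interval is planned: under the per-participant reading, one failure in 70 (1.4%) would be compatible with up to 7.7% (two-sided 95%), and that would not be shown. The tables are unremarkable in themselves. The problem is their combination with a safety criterion worded as absence.

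**Conclusion.** The point holds as a gap in what the plan can conclude about safety: no specified output bounds a harm rate. The bounds in step 1 rest only on 70 independent participants, all observed and exposed, and they loosen if fewer are exposed. The probabilities of an unseen harm rest on assumed rates and describe one type of event. They should not be quoted as the probability that the trial declares safety. The change is worth making because it decides whether a clean table is reported as evidence of safety or as a stated limit on risk.

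**What to change.** Make the same change in protocol section 9.1.1.1 and in the SAP rule for categorical variables:

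- Report the number and percentage of participants with any AE, with any device-related AE and with any SAE, each with an exact (Clopper-Pearson) 95% confidence interval.
- Use as denominator the number of participants actually exposed to the device, and show the ITT count alongside if wanted. Do not write 70 into the rule, since enrolment is approximate and some participants may never use the device.
- State the safety conclusion as the upper limit of the interval, not as absence of events.
- Keep all AEs in the summary whatever their judged relationship. Narrowing the criterion to device-related events would change the endpoint in a trial with no comparator to support attribution.

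The sponsor should also say whether the safety clause applies per participant or to the trial as a whole, since the interval does not settle that.

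The cost is a short wording change in each document and one extra column in the AE tables, with no new data or participants. The downside is a less favourable statement: with 70 exposed and no events of a given type, the report would say that rates up to about 5% are not excluded.

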#### **9.1.1.2 Secondary Criterion**

Percent change of spirometer reading from before treatment compared to three (3) hours after treatment by the participant. Subjective participant opinion of the efficacy provided by semi-weekly surveys.

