## **5.2 Secondary Objective**

To observe the quality of lung function that participants experience during the use of the device during the trial period.

Outcome measured by:

Percentage change of lung function. Evaluate expiratory forced vital capacity (FVC) and forced expiratory volume (FEV1) will be monitored with standard spirometer. Change from baseline before treatment and measure again up to 3.5 hours after treatment.

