#### **13.7.1.2.2 Data Transformation Before Analysis, If Any**

No data transformation will be applied to raw data.

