#### **13.7.2.2 Statistical Analysis of Secondary/Other Variables**

The secondary and other endpoints will be analyzed using the same statistical methodology as for the primary efficacy endpoint (except for weight and waist circumference).

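### FEV1 and FVC are expressed as percent change with no workable test named; if the mean individual percent change is judged against zero, reading error pushes it upward and no control arm cancels that

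*Protocol*

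**What the plan says.** Scale. Protocol 5.2 measures FVC and FEV1 by "Percentage change of lung function", from baseline to as late as 3.5 hours after treatment. Protocol 9.1.1.2 has "Percent change of spirometer reading from before treatment compared to three (3) hours after treatment by the participant". Protocol 9.1.1, under its primary heading, lists "changes in spirometer reading from before treatment compared to reading three (3) hours after treatment", without the word percent.

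Summary. The SAP's tables of continuous variables give "the minimum and maximum statistics, the arithmetic mean and median, the 95% confidence interval, standard deviation, and standard error". Protocol 13.4.1.3 also lists both mean and median.

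Test. Protocol 13.7.2.2 says: "The secondary and other endpoints will be analyzed using the same statistical methodology as for the primary efficacy endpoint". Only weight and waist circumference are exempted. The primary method in 13.7.1.2.3 is Kaplan-Meier with a two-sided log-rank test. Section 13.7.1.2.4 foresees formal 5% tests of two secondary endpoints once the primary is significant.

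Transformation. Protocol 13.7.1.2.2, within the primary analysis, says: "No data transformation will be applied to raw data".

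Design. There is one arm of about 70 participants, and 4.3 relies on each participant's own before/after comparison. Section 13.4.1.3 defines baseline as the single last reading before first device use. Section 8.11 pays participants for each day on which they send data, and 6.2 sets 21 days of participation. No section says how many before/after pairs are analysed or how they are combined.

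**The concern.** A percent change divides by the before-reading, which carries its own error. When that reading is too low the percent change is inflated, and when it is too high by the same amount the percent change is reduced by less. Suppose the true value is 100 before and after, the after-reading is exact, and the before-reading is 90 or 110 with equal chance. The two percent changes are +11.1% and −9.1%, which average +1.0% although nothing changed.

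A comparison arm measured in the same way would carry the same bias, and it would cancel in the difference. Here zero is the only reference. A confidence interval printed beside a mean percent change invites the reader to check whether it excludes zero, and with independent errors that check leans towards the device. Averaging more pairs narrows the interval but leaves the bias where it is.

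**Working it through.** **Plan's own figure.** There is none to reproduce: the documents give no effect size, SD, CV, power or error rate for spirometry.

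**Inputs from the documents.** n = 70, one arm, two-sided 5% level (2.5% in the direction of improvement), 21 days of participation.

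**Assumptions, not in the documents.** CV of one reading c = 3%, 5% or 10%; before/after pairs per person m from 1 to 21; mean true change zero; between-person SD of true change τ from 0 to 5%; participant-level one-sample t-test.

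**Step 1, bias.** Write before = μ(1 + e₁) and after = μ(1 + e₂), each error with CV c and mutual correlation ρ. Expanding the ratio to second order:

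E[after/before] − 1 ≈ c² − ρc² = c²(1 − ρ).

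With ρ = 0: 0.03² = 0.09%, 0.05² = 0.25%, 0.10² = 1.0%. With ρ = 0.5 each is halved. If the two CVs differ, the bias is c_before² − ρ·c_before·c_after.

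**Step 2, standard error of the mean percent change.**
- One pair each: √[(τ² + 2c²)/n]
- m after-readings against one baseline: √[(τ² + c²(1 + 1/m))/n]
- m fresh pairs averaged per person: √[(τ² + 2c²/m)/n]

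**Step 3, false-improvement rate** ≈ 1 − Φ(1.96 − bias/SE). For c = 5%, one pair, τ = 0: SE = √(0.005/70) = 0.845%; shift = 0.25/0.845 = 0.30; rate = 1 − Φ(1.66) = 4.8%.

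| Readings per person | CV | Formula, τ = 0 / τ = 5% | Simulation, τ from 0 to 5% |
|---|---|---|---|
| One pair | 3% | 3.7% / 3.3% | about 3–4% |
| One pair | 5% | 4.8% / 4.3% | about 4–5% |
| One pair | 10% | 8.6% / 8.0% | about 6–8% |
| 21 after, single baseline | 5% | 6.0% / 4.8% | about 4–6% |
| 21 after, single baseline | 10% | 12.7% / 11.0% | about 10–12% |
| 21 fresh pairs averaged | 5% | 27.3% / 5.9% | about 6–27% |
| 21 fresh pairs averaged | 10% | 77.4% / 29.6% | about 29–77% |

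The simulations used n = 70 and independent errors. Normal and lognormal errors gave similar results.

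**Step 4, alternatives under the same conditions.** The mean of log(after/before) gave a false-improvement rate of about 1.3% to 3%. Rates below 2.5% occur when τ > 0: if true percent changes average zero, their logs average about −τ²/2, or −0.125% at τ = 5%. The median percent change is close to zero with one pair each, but about +0.22% at CV 5% when six pairs are averaged per person first. A ratio of group means has a bias of about c²/n = 0.0025/70 = 0.004% at CV 5%.

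**Step 5, SpO2.** At an assumed CV of 1% the bias is 0.01² = 0.01%, which is negligible.

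**The case against.** The strongest reply is that the plan contains no such test. Sections 5.2 and 9.1.1.2 set only a scale. The SAP sentence describes summary tables and lists the median beside the mean. Section 9.1.1 speaks of changes, not percent changes. The method assigned to secondary endpoints is the log-rank test. This stands: a reader might infer that the arithmetic mean is the declared efficacy measure and that its 5% test is already inflated, but no section says either. It does not close the matter. A log-rank test compares groups, so one arm gives it nothing to compare, and it cannot analyse a continuous percent change. That leaves the tabulated mean, median and interval as the only usable spirometry results that the documents describe.

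A reader might also infer that the log scale is forbidden. The sentence on transformation sits under the primary analysis and concerns raw data. It reaches spirometry only through the carry-over in 13.7.2.2, or because 9.1.1 names spirometer changes under its primary heading. It is ambiguous rather than a clear ban.

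A third tempting reading is that the bias always favours the device and is large. Direction and size both depend on the errors. Positive correlation between same-day readings shrinks the bias, and a noisier, correlated after-reading could reverse it. The highest rates need 21 fresh pairs averaged per person and, at the very top, CV 10% with no between-person variation in true change. The documents specify none of this; 8.11 is only a payment clause. With the single baseline of 13.4.1.3 the inflation is much smaller.

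**Conclusion.** The point holds conditionally. If the mean of individual percent changes in FEV1 or FVC is tested, or its interval read, against zero, it is biased upward by about c² when before and after errors are independent, and nothing in a one-arm design removes it. With one pair and a CV of 3 to 5% the effect is small: a bias of 0.1 to 0.25% and a false-improvement rate of about 3 to 5% against 2.5%. It is moderate at CV 10% (about 6 to 8% with one pair, 10 to 12% with 21 after-readings and the single baseline). It is serious only if many fresh pairs are averaged. All of these rates rest on an assumed CV, number of pairs and spread of true change.

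The documents do not support the claim that the plan already commits to this estimator or test. They leave the estimator, the pairing of readings and a usable test undefined, so the biased route stays open. The point is worth acting on because the remedy is cheap, not because the bias has been shown to be large.

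**What to change.** In Protocol 5.2 and 9.1.1.2 and in the SAP:
- Analyse FEV1 and FVC as log(after/before), averaged per participant, with a one-sample two-sided 5% test and a 95% confidence interval, both back-transformed to a geometric mean percent change.
- State which before-reading is the baseline (the single reading of 13.4.1.3 or each day's own) and how repeated readings are combined.
- Exempt spirometry from the log-rank carry-over in 13.7.2.2.
- Limit the sentence in 13.7.1.2.2 so that it does not apply to spirometry.

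Absolute change or a ratio of group means would also avoid most of the bias. The log ratio is suggested because it still yields a percent change, the scale the plan asks for. SpO2 needs no change on this ground.

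The cost is a few sentences and a slightly smaller reported percent change. No additional participants, visits or measurements are needed.
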